THE VIABILITY OF SHORT STEMS IN TOTAL HIP ARTHROPLASTY

PRINCIPAL INVESTIGATOR:

[name]
Department of Orthopaedic Surgery
[name]
[name]

SUB-INVESTIGATORS:

[name]
Rosalind Franklin University

[name]
Northwestern University

[name]
Northwestern University

[name]
Northwestern University

Synopsis

| | |
|---------------------------------------|---|
| Title | The Viability of Short Stems in Total Hip Arthroplasty |
| Short Title | Short Stems Study |
| Protocol Date | 05/11/2015 |
| Study Duration | 3-3.5 years |
| Study Center(s) | Northwestern Memorial Hospital (NMH), Northwestern Memorial Faculty Foundation (NMFF) |
| Objectives | To determine the viability of short stems in THA |
| Number of Subjects | 75 |
| Diagnosis and Main Inclusion Criteria | Patients requiring total hip arthroplasty |

TABLE OF CONTENTS

| | |
|---|-------------|
| Synopsis..... | 2 |
| 1.0 Introduction..... | 4 |
| 2.0 Study Objectives..... | 5 |
| 3.0 Selection of Subjects | 5 |
| 3.1 Inclusion Criteria | 5 |
| 3.2 Exclusion Criteria..... | 5 |
| 4.0 Subject Registration..... | 5 |
| 5.0 Study Design & Methods..... | 5 |
| 6.0 Statistical Plan | 5 |
| 7.0 Data Collection & Record Keeping | 6 |
| 8.0 References | 7, 8 |
| Appendices..... | 9 |

1.0 INTRODUCTION - BACKGROUND AND RATIONALE

Porous-coated cementless stems were introduced in the late 1970s, in response to the high incidence of aseptic loosening associated with cemented stems (Judet et al 1978, Kavanagh et al 1989, Lord 1982, Stauffer 1982). The stem's porous surface achieves fixation via bony ingrowth at the endosteum (Engh et al 1987). In an effort to mimic the femur's natural stress distribution, many designs preferentially load the metaphysis (Joshi et al 2000). One such design is the proximally coated titanium tapered wedge, which is widely used today (Pitto et al 2010). Because loading is primarily dictated by bony ingrowth, the proximal porous coating avoids fixation at the diaphysis. The flat, tapered geometry reduces stiffness compared to cylindrical stems, thereby propagating stress to the proximal femur, rather than down the stem's axis (Engh et al 1987, Harvey et al 1999), (Boehm 1998). Further contributing to decreased stiffness is titanium's low elastic modulus, relative to that of cobalt-chromium (Harvey et al 1999, Mulliken et al 1996). Some contend the need for distal fixation in Dorr type C hips due to thin cortical bone at the metaphysis; however, proximally engaging stems have been shown to perform well in these patients (Kelly et al 2007, Reitman et al 2003).

If a stem's objective is to load proximally, then perhaps it need not extend into the diaphyseal canal. The emergence of short stems has initiated an alternative means of proximal loading, without the disruption of diaphyseal bone stock. The smaller incisions involved with short stem total hip arthroplasty (THA) reduce damage to muscle and soft tissue (Molli et al 2012). This enables a faster, more complete recovery for the patient, as well as a cosmetically superior result (Sherry et al 2003). Additionally, the preservation of bioavailable bone can be advantageous if a revision surgery is required (Toth et al 2010). Because short stems do not extend into the diaphysis, issues regarding proximal-distal mismatch of the femur are avoided (Patel et al 2013). This eases implantation and reduces the risk of intraoperative fracture (Azzam et al 2010, Cooper & Rodriguez 2010). The risk of intraoperative fracture is further mitigated because short stem THA does not require the use of reamers (Molli et al 2012, Scott et al 1975, Taylor et al 1978).

Although the standard-length proximally coated titanium tapered wedge has a successful long-term track record, its design leaves room for improvement (Mallory et al 2001, Marshall et al 2004). Standard length stems cause stress-shielding in Gruen zones 1 and 7, suggesting that the diaphyseal portion of a stem may interfere with proximal loading (Gibbons et al 2001, Schmidt et al 2004). Even proximally coated flat tapered stems are subject to diaphyseal loading (Cooper et al 2011). The Accolade stem has been associated with significant early subsidence, especially in males with Dorr type A hips (Jacobs & Christensen 2009). This suggests that the stem may wedge distally, thereby interfering with osseointegration (White et al 2012). By achieving a purely metaphyseal fit, short stems can prevent excessive bone loss secondary to stress shielding (Gustke 2012). We believe short stems are an equally effective alternative to traditional tapered stems in THA; however, long-term studies are essential to proving their efficacy.

Long-term studies of short stems are lacking in current literature. With respect to initial stability and bony ingrowth, short-term data is promising; however, there is still potential

for late aseptic failure (Capello et al 2009, Kroell et al 2009, Morales de Cano et al 2013, Schmidutz et al 2012). By conducting a single blinded, prospective, randomized investigation of two stems of varying length with equal metallurgy, coating, and proximal geometry, we can identify the effects of stem length on long-term outcomes.

2.0 OBJECTIVES

The goal of this study is to determine the viability of short femoral stems as an alternative to standard-length stems in total hip arthroplasty.

3.0 SELECTION OF SUBJECTS

3.1 INCLUSION CRITERIA

- Must require a total hip arthroplasty.
- Ages 18-85 years, regardless of gender, ethnicity, or pathology

3.2 EXCLUSION CRITERIA

- This study excludes any populations at risk.
- Minors, as well as any persons unable to consent, will not be eligible.

4.0 SUBJECT REGISTRATION

The subjects will be recruited by the PI and co-investigator at the orthopaedic surgery clinic in [name]. The study will be reviewed with the subjects and they will be consented by the PI, co-investigator, or other authorized study staff.

5.0 STUDY DESIGN & METHODS

50 patients will be recruited over 12-18 months. Half of the patients will receive the Taperloc Microplasty short femoral stem, while the other half will receive the standard-length Taperloc stem. Patients will be randomized in the operating room through the opening of opaque, study-numbered envelopes during preparation of the femur.

Immediate weight bearing will be allowed post-operatively. Patient-reported outcomes, as well as x-ray analysis, will be administered immediately post-operatively, 6 weeks post-operatively, 3 months post-operatively, 6 months post-operatively, 12 months post-operatively, and 2 years post-operatively. X-ray analysis includes antero-posterior pelvis, and lateral hip radiographs. The X-rays will be sent to [name] at the University of Innbruck, Austria for analyses using the EBRA-FCA software. Patient-reported outcomes will be measured using the Harris Hip and SF-36 questionnaires.

Procedures such as X-rays will be used during this research study to see how the patient is doing. The cumulative radiation exposure from these tests is considered small and is not likely to adversely affect the patient or their disease. However, the effects of radiation add up over a lifetime. It is possible that having several of these tests may add to the patient's risk of injury or disease. When deciding to enter this study, the patient should think about your past and future contact with radiation. Examples of contact with radiation include x-rays taken for any reason or radiation therapy for cancer treatment.

There are no other known risks involved in this study, aside from the minor inconvenience of completing questionnaires. One possible risk related with the patient's

participation in this study is the loss of privacy. To reduce these risks, all of the information collected will be de-identified (the patient will be assigned a study number and all data will be linked to that number and not the patient's name) and stored in a password protected file on a password protected computer. Some of the questions asked may be upsetting, or the patient may feel uncomfortable answering them. If the patient does not wish to answer a question, they may skip it and go to the next question.

Additionally, both stems used in this study are standard surgical stems used by orthopaedic surgeons. Therefore, there are no additional risks involved in the use of these stems for this study.

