6.0 STATISTICAL PLAN

This sample size is small enough to feasibly recruit over the given time period, yet large enough to correlate differences between the two groups. Antero-posterior pelvis and lateral hip radiographs will show patterns of stress-shielding, and the EBRA-FCA method provides a non-invasive means of measuring the extent of implant migration (if any). Patient-reported outcomes will be used to determine the effect of each implant on the patients' daily lives. Routine follow-up over 2 years is necessary to determine the long-term impact of each implant.

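### The synopsis sets the trial at 75 subjects and Section 5 at 50 patients, and nothing in the text reconciles the two

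*Combined protocol and SAP*

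**What the plan says.** The synopsis table gives "Number of Subjects | 75" and "Study Duration | 3-3.5 years". Section 5.0 (Study Design & Methods) gives a different total: "50 patients will be recruited over 12-18 months. Half of the patients will receive the Taperloc Microplasty short femoral stem". The remaining half are to receive the standard-length stem, so the design is two arms with equal allocation.

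Recruitment and randomisation happen at different points. Section 4.0 (Subject Registration) states "The subjects will be recruited by the PI and co-investigator at the orthopaedic surgery clinic", with consent taken by the study team. Section 5.0 then states "Patients will be randomized in the operating room through the opening of opaque, study-numbered envelopes during preparation of the femur".

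Section 6.0 (Statistical Plan) gives no number of its own. It says "This sample size is small enough to feasibly recruit over the given time period", adds that the sample is large enough for a comparison of the groups, and sets the follow-up: "Routine follow-up over 2 years is necessary to determine the long-term impact of each implant".

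**The concern.** The enrolment target tells the site when to stop recruiting and how many allocation envelopes to prepare. Here it has two values. If both count randomised patients, the 50th either completes enrolment or leaves the trial one third short, and patients 51 to 75 are either planned or over-enrolment.

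The rest of the plan cannot recover the intended number. The documents state no significance level, power, effect size, standard deviation or dropout rate, so neither 50 nor 75 can be derived. Section 6.0 argues that an unnamed number is both feasible and adequate, so a reader cannot be sure which total is being defended.

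**Working it through.** **Inputs from the documents.** Total 75 and duration 3 to 3.5 years (synopsis); total 50, recruitment over 12 to 18 months, equal split between two stems, six assessment times (Section 5.0); follow-up of 2 years (Sections 5.0 and 6.0).

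**1. Can either total be reproduced?** No. The design inputs are absent, so there is no calculation to repeat.

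**2. Does the timeline decide?** Recruitment plus follow-up is 12 + 24 = 36 months to 18 + 24 = 42 months, that is 3 to 3.5 years. This reproduces the synopsis duration, but the number of patients does not enter the sum, so it is the same for 50 and 75.

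**3. Size of the gap.** 75 − 50 = 25 patients, and 25/75 = 33%. By arm: 50/2 = 25; 75/2 = 37.5, in practice 37 and 38.

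**4. Could the two numbers count different things?**

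- *Dropout allowance.* Solving 50/(1 − d) = 75 gives d = 1 − 50/75 = 33.3%. Rates from 5% to 30% give 53 to 72 patients, never 75. The mistaken form 50 × (1 + d) = 75 needs d = 50%. Neither rate is stated.
- *Consented versus randomised.* This is possible in principle, because patients are recruited in clinic and randomised later in the operating room. But Sections 4.0 and 5.0 use the same verb for recruitment, and Section 5.0 divides its recruited 50 directly between the stems. A loss of 25 of 75 before surgery is nowhere mentioned.
- *Third arm.* Section 5.0 names only two stems, and Section 6.0 refers to two groups.

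**5. Does 75 fit the stated window?** Pace = patients / months.

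| Months | 50 patients | 75 patients |
|---|---|---|
| 12 | 4.17 per month | 6.25 per month |
| 15 | 3.33 per month | 5.00 per month |
| 18 | 2.78 per month | 4.17 per month |

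The two ranges meet at 50/12 = 75/18 = 4.17 per month. So 75 fits within 18 months only at or above the fastest pace that Section 5.0 implies for 50. At slower paces:

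- At 3.33 per month, 18 months yields 60 patients. Reaching 75 takes 75/3.33 = 22.5 months, and 22.5 + 24 = 46.5 months (about 3.9 years), which is 4.5 months beyond 42.
- At 2.78 per month, 75 takes 27 months, and 27 + 24 = 51 months (4.25 years), 9 months beyond 42.

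These paces are the planning target divided by its own window. The documents give no figure for site capacity.

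**6. Effect on precision, for illustration only.** The assumptions are not in the documents: a comparison of two means, equal variances and no loss to follow-up. The 95% confidence interval half-width, in SD units, is t × √(1/n₁ + 1/n₂).

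- 25 and 25: 2.011 × 0.2828 = 0.57 SD.
- 37 and 38: 1.993 × 0.2310 = 0.46 SD.

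**The case against.** The strongest reply is that the text, read closely, points to 50. Section 6.0 calls its sample feasible within a given period, and the only recruitment period in the documents is the one in Section 5.0: "50 patients will be recruited over 12-18 months". Section 6.0 follows directly on that section, so 50 is the natural antecedent. Equal halves also fit 50 exactly, whereas 75 would give 37.5 per arm. On this reading the synopsis cell is simply wrong, the repair is one line, and no power calculation or interim rule is disturbed because none is stated.

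Most of this stands as a lean towards 50. It does not prove that 50 is intended: Section 6.0 never states the number, and an odd total is often described loosely as halves. A likely explanation also does not remove the conflict for someone who works from the synopsis.

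Two criticisms of the figures are fair. The pace projections are conditional, because paces back-calculated from a target of 50 need not be what the site can achieve. The precision figures rest on assumptions from outside the documents. The finding depends on neither. It is also true that naming the number would not by itself make the feasibility statement verifiable, since no capacity figure is given; it would only show which total is being defended.

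**Conclusion.** The concern holds. Two current statements of the enrolment target, 75 and 50, differ by 25 patients, and nothing in the available text links them. This needs correction rather than tidying, because the target is a basic design figure and both values cannot be followed.

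The contradiction itself needs no assumption. Its practical effect is as described if both numbers count randomised patients; if they count different things, the plan does not say so. The contents list mentions appendices that were not available for this review, so the conclusion is limited to the text at hand. The documents lean towards 50 without settling the matter, and the choice belongs to the sponsor.

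**What to change.** The sponsor should confirm the intended number and state it, with its split by arm (25 and 25, or 37 and 38), in the synopsis, Section 5.0 and Section 6.0. The set of randomisation envelopes should match. If the two numbers count different things, for example patients consented and patients randomised, label each wherever it appears.

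**If 50 is confirmed:** wording only. Correct the synopsis and name the number in Section 6.0.

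**If 75 are to be randomised:** correct Section 5.0 and name the number in Section 6.0. This means 25 more patients than Section 5.0 plans, and 25 × 6 = 150 more scheduled assessments. The sponsor should also confirm that at least 4.17 patients per month are expected, in which case the window and duration stand. Otherwise both need revising: an extension of 4.5 months at 3.33 per month, or 9 months at 2.78 per month.

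### Harris Hip and SF-36 have no pre-operative baseline, so the patient-reported comparison loses precision and cannot show change from before surgery

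*Combined protocol and SAP*

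**What the plan says.** Section 5.0 names the instruments: "Patient-reported outcomes will be measured using the Harris Hip and SF-36 questionnaires". It gives one schedule for questionnaires and radiographs together: "Patient-reported outcomes, as well as x-ray analysis, will be administered immediately post-operatively, 6 weeks post-operatively, 3 months post-operatively", followed by "6 months post-operatively, 12 months post-operatively, and 2 years post-operatively". The list is complete as printed and contains no visit before the operation.

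The same section sets the time of allocation: "Patients will be randomized in the operating room through the opening of opaque, study-numbered envelopes during preparation of the femur".

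Section 6.0 states what the scores are for: "Patient-reported outcomes will be used to determine the effect of each implant on the patients' daily lives". It names no baseline, covariate, change score or model.

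Two other sections bear on the point. Section 3.1 admits a broad population: "Ages 18-85 years, regardless of gender, ethnicity, or pathology". Section 4.0 puts first contact before surgery: "The subjects will be recruited by the PI and co-investigator at the orthopaedic surgery clinic". It mentions no questionnaire at that contact.

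**The concern.** The first questionnaire follows both allocation and implantation. At that moment pain and mobility largely reflect the operation itself, and the score could also be affected by the stem. It therefore does not describe the patient's starting state, and it should not be used as an adjustment variable for a treatment comparison.

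The shared schedule probably explains the gap. For stem migration, an immediate post-operative film is the natural reference, because there is no stem to measure beforehand. That reasoning does not carry over to function and quality of life.

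Three things are at stake:

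- Differences between patients in starting function remain in the residual variance of a small trial. With a wide age range and any pathology admitted, those differences may be large, although the documents give no figure for the spread.
- The arms cannot be compared on starting function.
- Improvement from before surgery cannot be estimated for either stem.

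**Working it through.** **Inputs from the documents.** Section 5.0 gives 50 patients, half per stem, so 25 per arm. The synopsis gives 75, or 37.5 per arm on average, and is run as an alternative. The planned sample size cannot be reproduced, because Section 6.0 gives no alpha, power, effect size or SD.

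**Assumptions.** Two-sided alpha 0.05, no dropout, effects in SD units, a 0.5 SD difference for illustration, and a correlation r of 0.2 to 0.7 between the pre-operative and 2-year scores.

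**Step 1: variance.** Adjusting for the baseline by ANCOVA multiplies the residual variance by 1 − r². For example, at r = 0.5 this is 1 − 0.25 = 0.75. The number of unadjusted patients that would carry the same information as 50 adjusted ones is 50/(1 − r²); at r = 0.5, 50/0.75 = 66.7.

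**Step 2: power and detectable difference.** Power uses the two-sample t-test with standardised effect 0.5/√(1 − r²). The difference detectable with 80% power uses the normal approximation (1.96 + 0.84) × √(1 − r²) × √(2/n). Unadjusted with n = 25, this is 2.80 × 0.283 = 0.79 SD.

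| r | Variance factor | Equivalent of 50 | Power, 25 per arm | Detectable difference, 25 per arm | Power, total 75 |
|---|---|---|---|---|---|
| no baseline | 1.00 | 50 | 41% | 0.79 SD | 57% |
| 0.2 | 0.96 | 52 | 42% | 0.78 SD | 59% |
| 0.3 | 0.91 | 55 | 44% | 0.76 SD | 61% |
| 0.5 | 0.75 | 67 | 52% | 0.69 SD | 69% |
| 0.7 | 0.51 | 98 | 68% | 0.57 SD | 85% |

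**Step 3: cost of estimating the covariate.** At N = 50 this inflates the variance by about 1 + 1/46 = 1.022. The factors at r = 0.3, 0.5 and 0.7 become 0.93, 0.77 and 0.52. The pattern does not change.

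**Step 4: chance imbalance.** The SD of the difference in baseline means is √(2/25) = 0.283 SD. The chance that it exceeds 0.5 SD in either direction is 2 × P(Z > 0.5/0.283) = 2 × P(Z > 1.77) = 7.7%. With 75 patients it is 2 × P(Z > 0.5/0.231) = 3.0%. An imbalance of exactly 0.5 SD moves an unadjusted estimate by r × 0.5; at r = 0.5 that is 0.25 SD, half of the illustrative effect. This is the Step 1 variance seen within a single trial, not a second loss to add to it.

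**Step 5: type of analysis.** A simple change score has variance factor 2(1 − r): 1.4 at r = 0.3, 1.0 at 0.5 and 0.6 at 0.7. It beats the unadjusted comparison only when r exceeds 0.5, so the benefit depends on ANCOVA or an equivalent model.

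**The case against.** The best defence is that the arms are randomised, so an unadjusted comparison at 2 years is valid. The stated goal in Section 2.0 is short against standard stems, and no section names change from before surgery as an endpoint. That stands: the loss is in precision and interpretation, not validity.

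The size is also uncertain. The documents give no correlation, and at 0.2 or 0.3 the power gain is only about 1 to 3 percentage points with 25 per arm. If the synopsis total of 75 applies, unadjusted power is 57% and a large imbalance is less likely. These points limit the magnitude and should be stated with it.

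No section makes the questionnaires the primary outcome, and Section 6.0 has a larger gap in specifying no primary endpoint or model at all. A pre-operative score might also be taken in routine care. Neither point removes the problem: Section 6.0 assigns these scores a role, and the protocol neither requires nor plans to use a routine-care value. Section 4.0 does not say exactly when consent is taken. However, recruitment is in clinic and the envelope is opened in the operating room, so an opportunity before surgery can reasonably be inferred.

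**Conclusion.** The concern holds. The planned schedule contains no score taken before surgery or before allocation, and nothing elsewhere in the document supplies one. Followed as written, the trial gives up any estimate of improvement from before surgery, any check on the arms' starting function, and the precision that adjustment would bring.

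The omission is certain; the size of the precision loss is conditional on an assumed correlation. At 0.2 to 0.3 it is minor (4% to 9% of variance). At 0.5 to 0.7 it is material (25% to 49%), so that 50 patients with a baseline would be worth about 67 to 98 without one. Using the synopsis total of 75 changes the power levels but not the conclusion. The point is confined to the questionnaires and does not extend to stem migration. The change should be made, because it is cheap and the loss is irreversible once a patient has been operated on.

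**What to change.** - In Section 5.0, add Harris Hip and SF-36 at a clinic contact before surgery, ideally when consent is taken. Separate the questionnaire schedule from the radiograph schedule so that each has its own reference time.
- In Section 6.0, prespecify that 2-year scores are compared by ANCOVA with the pre-operative score of the same instrument as covariate, or by a mixed model over visits with that covariate. State that the immediate post-operative score is not used as a baseline and that a simple change score is not the main analysis.
- Reconcile the totals of 50 and 75, since the precision of this comparison depends on which applies.

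The cost is one more administration of forms already in use, a few minutes of patient time before surgery, and a sentence or two in Section 6.0.
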